1.4. Rationale for the Schedule of the Study

In this study nivolumab will be given once every 3 weeks (D1 of a 3 week cycle) and ABI-009 will be administered on D8 and D15 of the 3 week cycle starting in Cycle 2 (C2). Thus, ABI-009 will be given weekly for 2 weeks with a 1 week break.

Although nivolumab is approved on a biweekly schedule, in this study, because nivolumab is being given in combination with ABI-009 which is administered 2 out of 3 weeks, a 3 weekly schedule for nivolumab was adopted. In a prior Phase 3 combination study with ipilimumab, nivolumab 3 mg/kg was given every 3 weeks during the time when combination therapy was given (65). In this study, nivolumab and ABI-009 have different mechanisms of action. Therefore, it is not expected that the individual toxicities would significantly overlap. As a safety precaution, nivolumab will be given every three weeks (instead of every 2 weeks) when used in combination with ABI-009. Additionally, escalating doses of ABI-009 will start two dose levels below the MTD of 100 mg/m² observed in the Phase 1 study (44), as well as a de-escalation schedule if DLT is noted at Dose Level 1 (See Dose Reduction in [Section 6](#)).

Nivolumab acts by blocking PD1, a negative regulator of T cell activation and response, thus promoting T cell activation and allowing the immune system to attack the tumor (66). Rapamycin suppression of mTOR results in a multitude of effects including a disruption of the G1/S transition of the proliferation cycle and results in a mid-to-late G1 arrest (67). Rapamycin, by disrupting cytokine signaling that promotes lymphocyte growth and differentiation, also promotes the expansion of Treg cells and depletes effector T cells, leading to immune suppression (68). It was therefore hypothesized that administering anti-PD1 antibody first will allow T cell activation, which will not be blunted by later administration of ABI-009. On the other hand, the addition of ABI-009 after anti-PD1 antibody also allows ABI-009 to exert its antiproliferative activity and potentially to increase autophagy for enhanced antigen presentation (30). In a recent study with syngeneic B16 mouse tumor model testing the combination and sequencing of anti-PD1 antibody and ABI-009, the administration of anti-PD1 antibody for one week before combining with ABI-009 demonstrated better antitumor efficacy compared to anti-PD1/ABI-009 concurrent treatment or ABI-009 administered for one week before anti-PD1 antibody [privileged communication by AADi Bioscience Inc].

2. STUDY OBJECTIVES AND ENDPOINTS

2.1. Objectives

2.1.1. Primary Objectives

The primary objective of this study is to determine the maximum tolerated dose of ABI-009 when used in combination with nivolumab in advanced UPS, liposarcoma, osteosarcoma, chondrosarcoma and Ewing sarcoma.

2.1.2. Secondary Objectives

The secondary objectives are to investigate the disease control rate (DCR), progression free survival (PFS), recurrence-free survival (RFS) and overall survival (OS) using nivolumab/ABI-009 combination therapy in advanced Ewing's sarcoma, PEComa, epithelioid sarcoma, desmoid tumor, chordoma, non-small cell lung cancer, small cell lung cancer, urethelial carcinoma, melanoma, renal cell carcinoma, squamous cell carcinoma of head and neck, hepatocellular carcinoma, classical Hodgkin's lymphoma, MSI-H/dMMR metastatic colorectal cancer, and tumors with genetic mutations sensitive to mTOR inhibitors.

2.1.3. Exploratory Objectives

- To correlate DCR based on Immune-related Response Criteria (irRECIST) with that based on RECIST v1.1.
- To correlate DCR with PD-L1 and other biomarker expression in patients' tumors
- To correlate DCR with PTEN mutation in patient's archived tumor

2.2. Endpoints

2.2.1. Primary Endpoint

Maximum tolerated dose (MTD)

2.2.2. Secondary Endpoints

The secondary endpoints are

- Disease control rate (DCR), progression free survival (PFS), recurrence-free survival (RFS) as determined by the institution's radiologic assessment using Response Evaluation Criteria in Solid Tumors (RECIST) v1.1 and irRECIST criteria (Hodi et al., 2016); and overall survival (OS).
- PFS rate at 3, 6, 9, and 12 months, RFS at 4 months, median PFS, and median OS will be assessed separately in subgroups of patients with metastatic disease and locally advanced disease. Patients in the locally advanced tumor subgroup may be clinically indicated to receive surgery if there is sufficient tumor shrinkage, which could introduce a bias in the assessment of the PFS rate at 4 months, median PFS, and OS. Recurrence-free survival (RFS) defined as progression free

survival + absence of disease progression or recurrence after surgical resection has been added to the secondary endpoints to obviate this bias.

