End of Treatment	The date of the last dose of ABI-009 or nivolumab which ever is later for an individual patient.
End of Treatment Visit	For a patient is when safety assessments and procedures are performed after the last treatment, which must occur at least 4 weeks (\pm 7 days) after the last dose of ABI-009 or nivolumab whichever is later.
Primary Analysis	For this study will occur after all patients have either completed the study or completed 12 months of treatment. Patients who are still active at the time of the primary analysis may continue on study until disease progression or medication intolerance is observed.
Follow-up Period	The on-study time period after the End of Treatment Visit. All patients that discontinue study drug and have not withdrawn full consent to participate in the study will continue in the follow-up phase for survival and anticancer therapy. Follow up will continue approximately every 12 weeks (+/- 3 weeks), or more frequently as needed, until death, withdrawal of consent, or the study closes, whichever is the earliest. This evaluation may be made by record review and/or telephone contact.
Efficacy Analysis Dataset	All enrolled patients with measurable tumor per RECIST v1.1 at baseline who received at least two doses of ABI-009 and had a follow-up CT scan/MRI (modified treated population)
Full Analysis Set	All enrolled patients who receive at least one dose of ABI-009 (treated population).
Per-protocol Analysis Set	All enrolled patients who do not have any prospectively defined protocol violations.

Progression-free survival	The time from the first dose date to the first observation of a disease progression or death due to any cause.
Recurrence-free survival	The time from the first dose date to the first observation of disease progression or recurrence/progression after surgical resection, or death due to any cause.
Overall survival	The time from the first dose date to the date of death due to any cause.
Overall response rate	The proportion of patients who achieve a confirmed partial response or complete response per RECIST 1.1. Response rates based on a local radiologic assessment
Duration of response	The time from when criteria of response are first met until the first observation of disease progression per RECIST v1.1 or death due to any cause, whichever comes first.

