3.2. Inclusion Criteria

A patient will be eligible for inclusion in this study only if all of the following criteria are met:

1. Patients must have a histologically confirmed diagnosis of Ewing's sarcoma, PEComa, epithelioid sarcoma, desmoid tumor, chordoma, non-small cell lung cancer, small cell lung cancer, urethelial carcinoma, melanoma, renal cell carcinoma, squamous cell carcinoma of head and neck, hepatocellular carcinoma, classical Hodgkin's lymphoma, MSI-H/dMMR metastatic colorectal cancer, and tumors with genetic mutations sensitive to mTOR inhibitors, that is either metastatic or locally advanced and for which surgery is not a recommended option.
2. Patients must have one or more measurable target lesions by CT scan or MRI. Measurable disease by RECIST v1.1, confirmed by investigator.
3. Previously treated patient with Ewing's sarcoma, PEComa, epithelioid sarcoma, desmoid tumor, chordoma, non-small cell lung cancer, small cell lung cancer, urethelial carcinoma, melanoma, renal cell carcinoma, squamous cell carcinoma of head and neck, hepatocellular carcinoma, classical Hodgkin's lymphoma, MSI-H/dMMR metastatic colorectal cancer, and tumors with genetic mutations sensitive to mTOR inhibitors, if treatment is completed after 5 half-lives or ≥ 28 days prior to enrollment, whichever is shorter.
4. Eligible patients, 12-17 years (≥ 40 kg) or 18 years old or older, with Eastern Cooperative Oncology Group (ECOG) performance status 0 or 1.
5. Patients must have the following blood chemistry levels at screening (obtained ≤ 14 days prior to enrollment (local laboratory):
 - a. total bilirubin $\leq 1.5 \times$ upper limit of normal (ULN) mg/dl

- b. AST/ALT $\leq 2.5 \times$ ULN ($\leq 5 \times$ ULN if attributable to liver metastases); alk phos $< 3 \times$ ULN (patients with alk phos > 3 ULN will be allowed if due to bone metastases) AST $\leq 2.5 \times$ ULN ($\leq 5 \times$ ULN if attributable to liver metastases)
- c. serum creatinine $\leq 1.5 \times$ ULN

6. Adequate biological parameters as demonstrated by the following blood counts at screening (obtained ≤ 14 days prior to enrollment, local laboratory):

- a. Absolute neutrophil count (ANC) $\geq 1.5 \times 10^9/L$; b. Platelet count $\geq 100,000/mm^3$ ($100 \times 10^9/L$); c. Hemoglobin ≥ 9 g/dL.

7. Serum triglyceride < 300 mg/dL; serum cholesterol < 350 mg/dL.

8. Male or non-pregnant and non-breast feeding female:

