8.3. Efficacy Analysis

The Efficacy Analysis Dataset includes all enrolled patients with measurable tumor per RECIST v1.1 at baseline who receive at least two doses of ABI-009 and had a follow-up CT scan/MRI.

The disease control rate (DCR; CR+PR+SD), objective response rate (ORR; CR + PR), progression free survival (PFS), recurrence-free survival (RFS) will be assessed by an local radiologic assessment using Response Evaluation Criteria in Solid Tumors (RECIST) v1.1.

The focus of the study is to estimate the DCR in patients treated with ABI-009 and nivolumab. Patients who progress before receiving ABI-009 will be replaced, and will not be included in the statistical analysis. The number and percentage of patients achieving disease control (CR, PR or SD) will be summarized.

Analysis of other efficacy endpoints, PFS at 4 months, RFS at 4 months, median PFS, median RFS and median OS will be assessed for all subtypes together, and separately in the five sarcoma subtypes with metastatic disease and locally advanced disease. Patients may be stratified further as locally advanced or metastatic. Patients in the locally advanced tumor subgroup may be clinically indicated to receive surgery if there is sufficient tumor shrinkage, which could introduce a bias in the assessment of the PFS at 4 months, median PFS, and OS. Recurrence-free survival (RFS) defined as progression free survival + absence of disease progression or recurrence after surgical resection has been added to the secondary endpoints to obviate this bias.

PFS, RFS and OS will be summarized using Kaplan-Meier (KM) analysis. The number of patients in each category is expected to be small; therefore, PFS at 4 months, RFS at 4 months, median PFS, and median OS for these patients will be summarized by descriptive statistics.

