8.5. Covariates and Subgroups

Up to 20 clinical indications will be studied, including Ewing's sarcoma, PEComa, epithelioid sarcoma, desmoid tumor, chordoma, non-small cell lung cancer, small cell lung cancer, urothelial carcinoma, melanoma, renal cell carcinoma, squamous cell carcinoma of head and neck, hepatocellular carcinoma, classical Hodgkin's lymphoma, MSI-H/dMMR metastatic colorectal cancer, and tumors with genetic mutations sensitive to mTOR inhibitors, as well as those with metastatic disease and those with locally advanced disease for which surgery is not an option. The subgroups of patients will be assessed together and as subgroups for the efficacy endpoints.

In addition, the following covariates may be used to examine efficacy and/or safety in subgroup or covariate analyses, if sufficient number of patients are enrolled in the subgroups:

- Gender (male and female)
- Age at enrollment (<65 vs ≥65 and <75 vs ≥75 years)
- ECOG Performance Status at baseline (0 vs 1)

- Time from initial diagnosis to enrollment

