8.8.2. General Considerations

The secondary efficacy endpoint, DCR, will be determined by a local radiologic assessment.

The primary analysis will evaluate the DCR in patients treated with ABI-009 and nivolumab by providing the number and proportion of patients achieving disease control along with an exact binomial 95% CI for the proportion.

DCR is defined as the proportion of patients who achieve a confirmed CR, PR or SD per RECIST v1.1. If an initial observation of objective response (CR or PR) is made, a confirmation scan should be done at 6 weeks after initial observation.

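### Classical Hodgkin's lymphoma is eligible and pooled with the other indications, but its response and progression are scored only by solid-tumour criteria

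*Combined protocol and SAP*

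**What the plan says.** Eligibility: inclusion criterion 1 in Section 3.2 lists, among other histologies, "hepatocellular carcinoma, classical Hodgkin's lymphoma, MSI-H/dMMR metastatic colorectal cancer, and tumors with genetic mutations sensitive to mTOR inhibitors". Criterion 2 applies to all patients: "Measurable disease by RECIST v1.1, confirmed by investigator".

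Objective: Section 2.1.2 seeks DCR, PFS, RFS and OS in a list that includes "squamous cell carcinoma of head and neck, hepatocellular carcinoma, classical Hodgkin's lymphoma, MSI-H/dMMR metastatic colorectal cancer".

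Criteria: Section 2.2.2 has DCR, PFS and RFS assessed "as determined by the institution's radiologic assessment using Response Evaluation Criteria in Solid Tumors (RECIST) v1.1 and irRECIST criteria". Section 5.2.4 evaluates CT or MRI scans under RECIST v1.1 and also obtains irRECIST. Section 8.3 assigns DCR, ORR, PFS and RFS to "local radiologic assessment using Response Evaluation Criteria in Solid Tumors (RECIST) v1.1". Section 8.8.2 states: "DCR is defined as the proportion of patients who achieve a confirmed CR, PR or SD per RECIST v1.1". The definitions table gives overall response rate as "The proportion of patients who achieve a confirmed partial response or complete response per RECIST 1.1".

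Pooling: Section 8.5 names classical Hodgkin's lymphoma in its list of indications and then says: "The subgroups of patients will be assessed together and as subgroups for the efficacy endpoints".

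**The concern.** The protocol spells out RECIST as criteria for solid tumours, then applies them without exception to an eligible lymphoma. It gives neither an alternative criterion nor a reason for using the same one. This is a stated rule that does not fit one of the diseases it governs, so it is more than a missing detail.

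It reads like a leftover from an earlier scope. The synopsis still gives the indication as sarcoma, and Sections 8.3 and 8.8.3 still break results down by five sarcoma subtypes. Lymphoma appears in the eligibility criteria, the objective and the subgroup list, but the response criteria were not adapted to it.

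Two things are at stake. A response rate or PFS reported for the lymphoma subgroup would not be a lymphoma response rate or PFS. The same patients also enter the pooled DCR, ORR, PFS and RFS and the comparison of RECIST with irRECIST in Section 8.4. DCR is not marginal here: Section 8.3 calls its estimation the focus of the study, and Section 8.8.2 has the primary analysis report it with an exact interval.

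**Working it through.** **Step 1: is there an exception anywhere?** Set side by side, the sections give:

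| Item | Section | Treatment of classical Hodgkin's lymphoma |
|---|---|---|
| Eligibility | 3.2, criteria 1 and 3 | named |
| Measurability | 3.2, criterion 2 | RECIST v1.1, all patients |
| Objective | 2.1.2 | named for DCR, PFS, RFS, OS |
| DCR, PFS, RFS | 2.2.2 | RECIST v1.1 and irRECIST |
| Image evaluation | 5.2.4 | RECIST v1.1; irRECIST also obtained |
| DCR, ORR, PFS, RFS | 8.3 | RECIST v1.1 |
| DCR definition | 8.8.2 | RECIST v1.1 |
| ORR definition | definitions table | RECIST v1.1 |
| Efficacy Analysis Dataset | 8.3 | RECIST-measurable at baseline; no restriction by histology |
| Pooling | 8.5 | named; pooled and as a subgroup |

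No row gives a lymphoma criterion, an exemption or an exclusion from pooling. The breakdown by five sarcoma subtypes in 8.3 and 8.8.3 would not contain lymphoma, but the analysis of all subtypes together in 8.3 and the subgroup analysis in 8.5 would.

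**Step 2: how far can a pooled rate move?** The plan states no figure to reproduce on this point. If k of n pooled patients have lymphoma and every one of them changes category in the same direction, the pooled proportion moves by k/n. The documents give 22–28 evaluable patients in phase 2 (Section 3.1) and 40–50 enrolled in all (synopsis). They do not give k, so k = 1, 2, 3 is an assumption. The last column is the exact binomial 95% interval (the method in Section 8.8.1) at an observed rate of 50%, for comparison.

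| n | k = 1 | k = 2 | k = 3 | Exact 95% CI at 50% |
|---|---|---|---|---|
| 22 | 4.5 points | 9.1 | 13.6 | 28.2–71.8% |
| 28 | 3.6 | 7.1 | 10.7 | 30.6–69.4% |
| 40 | 2.5 | 5.0 | 7.5 | 33.8–66.2% |
| 50 | 2.0 | 4.0 | 6.0 | 35.5–64.5% |

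Counting evaluable patients over both phases, n runs from 12 + 22 = 34 to 18 + 28 = 46. One patient is then 100/34 = 2.9 to 100/46 = 2.2 points.

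**Step 3: a benchmark for k.** Section 8.5 lists 15 categories. Under an even spread, k = n/15, so the bound is (n/15)/n = 1/15 = 6.7 points whatever n is. Section 8.5 also allows up to 20 indications, which would give 1/20 = 5.0 points. If no lymphoma patient enrols, it is zero.

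**Step 4: why k/n is a ceiling.** ORR counts CR and PR; DCR counts CR, PR and SD. A patient relabelled between CR and PR changes neither. ORR moves only when a patient crosses PR/SD, and DCR only when a patient crosses SD/PD. The documents do not show how often a lymphoma criterion read from the same scans would produce such crossings.

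**Step 5: the other endpoints.** For PFS and RFS, the progression dates of k patients rest on RECIST; deaths do not. OS depends on date of death alone, and MTD on toxicity.

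**The case against.** The best case for the plan is that one common scale is a coherent choice in a descriptive basket study. Entry requires RECIST-measurable disease, so a score can be computed for every lymphoma patient and nothing will be missing. Section 8.6 already says the sample is too small for statistical conclusions. The trial runs at a single sarcoma centre, so zero or one lymphoma patient is plausible, and at small k the possible shift lies well inside the exact interval.

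Most of this stands for the pooled rates. It does not rescue the subgroup: a score that can be computed is not thereby one made for the disease, and an interval describes sampling error, not a category that does not fit. The plan also gives no rationale for a common scale.

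Three stronger readings are tempting but not supported. A reader might infer that the pooled DCR, ORR and PFS as a whole are on the wrong scale; only the lymphoma share is. A reader might infer that the secondary objective cannot be answered for lymphoma; OS is part of that objective and does not depend on RECIST. A reader might also infer a definite bias of known size or direction. The documents support only the ceiling k/n, and the names of the criteria are the only evidence in them of misfit.

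**Conclusion.** The point holds with limited scope. The response and progression results of the lymphoma subgroup are wholly affected, because they rest on criteria the protocol itself names as being for solid tumours. In the pooled DCR and ORR the effect is at most k/n: 2.0 to 4.5 points per lymphoma patient for n from 50 down to 22, about 6.7 points under an even spread over the 15 listed categories, and zero if none enrol. Reaching the ceiling requires every lymphoma patient to cross the relevant boundary in the same direction. The number of lymphoma patients and the even spread are assumptions. The lymphoma share of pooled PFS and RFS and of the RECIST versus irRECIST comparison has the same weakness. MTD and OS are unaffected, and no sample size or power figure changes, since none is stated for efficacy.

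The change is worth making because it is cheap and lets the trial report an interpretable lymphoma response.

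**What to change.** - In Sections 2.2.2, 5.2.4, 8.3 and 8.8.2, state that response and progression in classical Hodgkin's lymphoma are assessed with a named lymphoma-specific CT-based criterion, read locally from the scans already scheduled. Since Section 5.2.4 allows CT or MRI, say how a patient followed by MRI is read. Carry the change into the synopsis and the definitions table.
- Report the lymphoma results separately.
- Give the pooled RECIST-based DCR, ORR, PFS and RFS with and without lymphoma patients. This respects the pooling in Section 8.5 and shows how much depends on them; removing treated patients from the pooled analysis altogether would be less sound.
- Leave lymphoma patients out of the RECIST versus irRECIST comparison in Section 8.4.
- Align inclusion criterion 2 and the Efficacy Analysis Dataset, so that measurability for lymphoma refers to the criterion used for lymphoma.

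The cost is protocol and SAP wording, one extra scoring form for a few patients at most, and a slightly smaller denominator in the analysis without lymphoma. No additional scans or readers are needed.

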2.2.3. Exploratory Endpoints

- Correlation between DCR based on Immune-related Response Criteria (irRECIST) with that based on RECIST v1.1.
- Correlation between DCR with PD-L1 and other biomarker expression in patients' tumors.
- Correlation between DCR and PTEN mutation in patient's archived tumor

2.3. Study Design

This is an open label, dose-seeking phase 1/2 study using a defined dose of nivolumab and escalating doses of ABI-009 given intravenously.

I. Dose Escalation Phase 1 Part of Study: The study will employ the standard "cohort of three" design (Storer, 1989). Three patients are treated at each dose level with expansion to six patients per cohort if DLT is observed in one of the three initially-enrolled patients at each dose level. If no DLT occurs after 2 doses, escalation to the next dose level will be permitted. The maximum tolerated dose is defined as the highest safely tolerated dose, where not more than one patient experienced DLT, with the next higher dose level having at least two patients who experienced DLT. Patients in the dose escalation study may continue treatment at their designated dose levels up to eighteen 3-week treatment cycles or until significant disease progression or unacceptable toxicity occurs. No intra-patient dose escalation will take place.

Dose of nivolumab: 3 mg/kg IV over 30 min. q 3 weeks

NB: ABI-009 will start after 2nd Nivo dose, and will be administered on D8 and D15 beginning in C2.

Dose of ABI-009: Escalating doses IV over 30 min for 2 of every 3 weeks:

Treatment Cycle	# Pts.	Dose Level	Dose, mg/m2
Every 3 weeks	3-6	I	56
Every 3 weeks	3-6	II	75
Every 3 weeks	3-6	III	100

Note: DLT includes any \geq Grade 3 colitis, hepatitis, or pneumonitis, any Grade 1-2 colitis, hepatitis or pneumonitis that recurs, worsens or persists with oral steroids longer than 14 days, symptoms of adrenal crisis, any Grade 4 hematologic toxicity or any \geq Grade 3 non-hematologic toxicity.

II. Expansion Phase 2 Part of Study: Following dose escalation, an additional 22-28 patients will receive ABI-009 at the MTD and defined doses of nivolumab to assess overall safety and potential efficacy in a greater number of patients. Patients in the expansion

phase of the study may continue treatment up to 18 3-week treatment cycles or until significant disease progression or unacceptable toxicity occurs.

The study will be conducted in compliance with International Conference on Harmonisation (ICH) Good Clinical Practices (GCPs).

Surgical Resection: After three or more treatment cycles, the principal investigator may recommend surgical debulking, complete surgical removal or a biopsy. If residual disease is present either by histopathological examination or by CT scan/MRI, repeat treatment cycles may be given 2-4 weeks after surgery, if the surgical incision has healed, and if the patient has \leq grade I toxicity.

Resected or biopsied tumors will be analyzed for the effects of this dual therapy on disease control rate, and immune cell trafficking in the tumor microenvironment. Fresh and paraffin embedded tissue blocks will be analyzed by FACS for PD-L1 and other biomarkers, including Tregs, CD8+, CD4+ cells etc. Immunohistochemistry for cyclin G1, cyclin D1 and Ki67 will be conducted to determine the tumor's proliferative state. Histopathologic examination for tumor necrosis and mitotic index will also be determined.

Conditions for Continuation of Treatment in the Presence of Increased Tumor Size by CT scan or MRI Indicating Progressive Disease by RECIST v1.1:

Treatment may be continued if:

1. There are no signs or symptoms indicating unequivocal progression.
2. There is no worsening of ECOG score attributable to progressive disease.
3. There is no tumor growth at critical sites that is life-threatening.
4. Patient signs an informed consent that he/she is aware of alternative therapies but wishes to defer these therapies.
5. There is clinical benefit, as determined by investigator

